### 2.4. Framework

No superiority hypothesis testing framework will be used.

### 2.5. Statistical interim analyses and stopping guidance

No formal interim analyses of the primary outcome were pre-specified in the study protocol; thus, no formal stopping guidance has been established. However, basic descriptive analyses have been conducted after the inclusion of the first 20 participants, specifically to support grant applications and funding justification. These preliminary analyses were limited to feasibility indicators and secondary outcomes, and were not used to assess efficacy. Additionally, preliminary descriptive results for selected secondary outcomes were presented at national and international scientific conferences. Importantly, none of these analyses involved inferential testing of the primary outcome, and no modifications to the study protocol, including endpoints or procedures, were made because of these preliminary findings.

### 2.6. Timing of the final analyses

The final analyses will be performed after the finalization of the data collection and processing of the primary and some secondary outcomes.

### 2.7. Timing of outcome assessment

Primary outcome (CCI) and other clinical prognosis outcomes will be assessed 30 days postoperatively, 3 months after the surgery and 1 year after the surgical procedure. All other secondary outcomes will be measured at baseline, preoperatively (i.e., 1 day before surgery), 3 months after surgery, and 1 year after surgery.

## 3. Statistical principles

### 3.1. Confidence and P values

All statistical tests will be two-tailed, with a significance level set at  $\alpha = 0.05$ . Corresponding 95% confidence intervals will be reported. No adjustments for multiplicity will be applied, as only one primary outcome has been pre-specified and all secondary and exploratory analyses are considered hypothesis-generating.

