### 2.3. Sample size

In a previous study, a 17.3-point mean difference was detected in CCI between a group of patients who were physically inactive and a group who were regularly active, both undergoing colorectal cancer surgery (2). Therefore, this study sample size was estimated for an  $\alpha$  level of 0.05 and 90% power to detect a 17.3-point difference in CCI (primary outcome) between usual care and PPP groups, considering an  $\sigma$  of 25.2 (the CCI standard deviation of the group of participants who were physically inactive). Based on this data, a sample of 36 participants per group was considered sufficient for our analysis. However, assuming a 20% drop-out rate, we decided to recruit a total sample size of 45 participants for each study group. Thus, a total of 90 participants ( $n \approx 45$  women) will be enrolled in the ONCOFIT study.

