## 5. Analysis

### 5.1. Outcomes definition

#### Primary outcomes

**CCI** obtained by patients at 30 days and 3 months after the surgical procedure.

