#### Secondary outcomes

1. **CCI** scores obtained at 1 year post-surgery.
2. **Proportion of patients experiencing at least one complication** within 30 days, 3 months and 1 year post-surgery.
3. **Proportion of patients experiencing at least one medical complication** within 30 days, 3 months and 1 year post-surgery.
4. **Proportion of patients experiencing at least one surgical complication** within 30 days, 3 months and 1 year post-surgery.
5. **Hospital readmissions occurring** within 30 days, 3 months and 1 year post-surgery.
6. **Urgency visits** within 30 days, 3 months and 1 year post-surgery.
7. **Hospital length of stay**, defined as the total number of days the patient remains admitted in the hospital following the surgical procedure.
8. **Quality of Recovery Short-form Questionnaire (QOR-15)** measured 24, 48 and 72 hours after the surgical procedure.
9. **Change in body weight** (Baseline, preoperatively, 3 months after surgery and 1 year after surgery). Body weight will be measured by a digital scale.
10. **Change in body height** (Baseline, preoperatively, 3 months after surgery and 1 year after surgery). Body height will be measured by a stadiometer.
11. **Change in fat mass** (Baseline, preoperatively, 3 months after surgery and 1 year after surgery). Fat mass will be assessed by Dual-energy X-ray Absorptiometry (DXA).
12. **Change in fat free mass** (Baseline, preoperatively, 3 months after surgery and 1 year after surgery). Fat free mass will be assessed by Dual-energy X-ray Absorptiometry (DXA).
13. **Change in bone mineral density** (Baseline, preoperatively, 3 months after surgery and 1 year after surgery). Bone mineral density will be assessed by Dual-energy X-ray Absorptiometry (DXA).
14. **Change in waist circumference** (Baseline, preoperatively, 3 months after surgery and 1 year after surgery). Waist circumference will be measured following the procedures outlined by the International Society for the Advancement of Kinanthropometry.
15. **Change in hip circumference** (Baseline, preoperatively, 3 months after surgery and 1 year after surgery). Hip circumference will be measured following the procedures outlined by the International Society for the Advancement of Kinanthropometry.
16. **Change in neck circumference** (Baseline, preoperatively, 3 months after surgery and 1 year after surgery). Neck circumference will be measured following the

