### 5.2. Analyses methods

The main analyses for primary and secondary outcomes will follow the intention-to-treat approach. For the primary outcome, given the commonly observed non-normality distribution of the data in this fields, a Mann-Whitney U test will be used to compare the median CCI between the intervention and control groups. For secondary outcomes with a single time-point (e.g., hospital lenght of stay), comparisons between groups will also be conducted using Mann-Whitney U test. To assess whether the group allocation (intervention/control) influences the risk of postoperative complications (yes/no), a binary logistic regression model will be conducted. Regarding secondary outcomes at multiple time points, a linear mixed-effects models with individual measures of growth being modelled as the function of randomly assigned group, assessment time, and the interaction between group and time. Estimations will be performed using the restricted maximum-likelihood method, including an unstructured covariance matrix to adjust for within-participant clustering resulting from the repeated-measures design. This model will assume that missing values are missing-at-random.

Secondary analyses will be performed using the per-protocol approach, defined as attending >80% of the sessions offered to the intervention group.

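### Multiplicity control is waived because there is one primary outcome, yet CCI is primary at both 30 days and 3 months and no rule says which result decides the trial

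*SAP*

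**What the plan says.** - **Section 3.1** sets all tests as two-tailed at 0.05 and then says "No adjustments for multiplicity will be applied, as only one primary outcome has been pre-specified". Its second ground, that other analyses are hypothesis-generating, covers only secondary and exploratory analyses.
- **Section 5.1, Primary outcomes**, lists CCI "obtained by patients at 30 days and 3 months after the surgical procedure". Under Secondary outcomes, the first item is CCI "scores obtained at 1 year post-surgery".
- **Section 2.3** sizes the trial for "90% power to detect a 17.3-point difference in CCI (primary outcome) between usual care and PPP groups", without a time point.
- **Section 2.7** gives the assessment times: CCI "will be assessed 30 days postoperatively, 3 months after the surgery and 1 year after the surgical procedure".
- **Section 5.2** says that for the primary outcome "a Mann-Whitney U test will be used to compare the median CCI between the intervention and control groups", again without a time point. Mixed models are kept for secondary outcomes measured repeatedly.

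**The concern.** Two time points are placed in the primary category and a third is deliberately kept out of it. The waiver in 3.1 counts one primary outcome, but multiplicity depends on how many tests can support the primary claim, not on how many instruments are used. Two tests at 0.05 each is the likely reading of 3.1 together with 5.1, though the SAP does not say so outright.

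What is at stake is the meaning of a positive trial. If 30 days and 3 months disagree, a positive and a negative conclusion could each be presented as pre-specified. If either result suffices, the stated 5% error rate does not hold.

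**Working it through.** **1. Does any section settle the rule?**

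| Section | Time point for primary CCI | Decision rule |
|---|---|---|
| 2.3 Sample size | none named | none |
| 2.7 Timing | 30 days, 3 months, 1 year (schedule only) | none |
| 3.1 P values | none named; counts one primary outcome | no adjustment |
| 5.1 Primary outcomes | 30 days and 3 months | none |
| 5.2 Methods | none named; one Mann-Whitney test | none |

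A Mann-Whitney test compares one value per patient, so the test in 5.2 cannot combine the two time points.

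**2. The plan's own figure.** Inputs from 2.3: difference 17.3, SD 25.2, alpha 0.05, power 90%, 36 per group, 20% drop-out.

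- Formula: n per group = 2 × [SD × (z_alpha + z_power) / difference]².
- Two-sided: 2 × [25.2 × (1.960 + 1.282) / 17.3]² = 44.6, so 45.
- One-sided: 2 × [25.2 × (1.645 + 1.282) / 17.3]² ≈ 36.3, so 37, close to the stated 36.
- Drop-out: 36 / 0.80 = 45, which matches.

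The stated 36 is thus approached only with a one-sided test, whereas 3.1 requires two-sided tests. That is a separate matter. It is noted because it, and not multiplicity, explains why power at 36 per group appears below as 82% and not 90%.

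**3. False-positive rate with no effect at either time.** Each test is two-sided at 0.05.

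- P(either) = 0.05 + 0.05 − P(both), where P(both) = P(|Z1| > 1.96 and |Z2| > 1.96) for bivariate normal statistics with correlation ρ.
- The SAP gives no ρ, so it is an assumption.

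| ρ (assumed) | P(both) | P(either) |
|---|---|---|
| 0 | 0.0025 | 0.0975 |
| 0.7 | 0.0165 | 0.0835 |
| 0.8 | 0.0219 | 0.0781 |
| 0.9 | 0.0296 | 0.0704 |
| 0.95 | 0.0354 | 0.0646 |

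**4. Check with the planned test.** Pairs of Mann-Whitney tests were simulated on CCI accumulating from 30 days to 3 months (20,000 runs per scenario, 36 or 45 per arm). The assumptions were 50% to 70% of patients with a zero score at 30 days and 3% to 30% with a later event. Either test was significant in 5.6% to 8.0% of runs, and both in 1.5% to 4.1%.

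**5. Power under each possible rule.** Two-sided t-test, standardised difference 17.3 / 25.2 = 0.687. Rows involving both time points assume equal effects at both and ρ from 0.7 to 0.95.

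| Rule | 45 per group | 36 per group |
|---|---|---|
| One lead time point at 0.05 | 90% | 82% |
| Single test at 0.025 (Bonferroni) | 83% | 73% |
| Holm, a given time point | 86–87% | 76–78% |
| Holm, at least one | 87–91% | 77–84% |
| Both required at 0.05 | 84–87% | 74–79% |

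The Holm figures for a given time point come from simulated t-tests (100,000 runs per setting). They exceed the Bonferroni figures because Holm releases the full 0.05 to the second test once the first succeeds. Mann-Whitney power will differ from all of these.

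**The case against.** The SAP nowhere says that either time point may carry the claim. Its singular wording (one primary outcome, one test, one powered difference) can be read as one variable observed at two times. If both had to succeed, no adjustment would be needed. Because the scores come from the same patients, the two tests are probably strongly correlated, so 9.75% is not a realistic figure. The protocol, not seen here, may name the leading time point. Section 2.5 also states that "none of these analyses involved inferential testing of the primary outcome".

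Part of this stands. An undefined decision rule is shown; an inflated error rate follows only under the either-counts reading, and it is then modest. Section 2.7 is an assessment schedule and need not change.

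The rest does not remove the problem. Calling CCI one variable does not reduce the number of tests. Whatever the protocol says, 3.1 and 5.1 conflict within the SAP. Section 2.5 rules out inferential testing of the primary outcome but reports descriptive looks at secondary outcomes. That category includes complication proportions at 30 days and 3 months, which are closely related to CCI, and the SAP does not say whether they were among the results seen.

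**Conclusion.** The concern holds and must be fixed. The justification in 3.1 is wrong against 5.1, and the SAP does not define what makes the trial positive. Under an either-counts rule the false-positive rate is 6.5% to 8.3% for assumed correlations of 0.95 to 0.7, with 9.75% as the ceiling for non-negative correlation. Simulation of the planned test gives 5.6% to 8.0% under assumed event rates. Under a both-required rule the rate never exceeds 5%. The textual conflict depends on no assumption; only the size of the inflation does. The seriousness lies more in a success criterion that can be chosen after the results are seen than in the size of the excess over 5%.

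**What to change.** Before CCI is compared by arm, amend 5.1, 5.2 and 3.1 to one rule, checked against the protocol:

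- **(a) One primary time point.** List the other as secondary, as is already done for 1 year, which makes 3.1 true as written; or test it second in a fixed sequence at two-sided 0.05. The lead test keeps its alpha and power. In the sequence, the other time point is confirmatory only if the first succeeds.
- **(b) Holm across the two.** The first step is at 0.025, at the cost in power shown above.
- **(c) Both required.** Each test stays at 0.05, and power for the joint claim is as shown above.

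Which time point leads is the sponsor's choice. Section 5.2 should then name the time point of each CCI test, and 2.3 the time point or rule that the power refers to. Date the amendment, state that no comparison of CCI by arm had been seen, and list which secondary outcomes were examined in the preliminary analyses of 2.5. The change is wording only and needs no new data. Option (a) costs least.

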### 3.2. Adherence, attendance, compliance and protocol deviation

Attendance will be defined as the % of sessions attended by the participants (recorded by trainers) divided by all the offered sessions (varying on patient preoperative and postoperative periods duration). Compliance will be defined as the % of sessions in which the amount of time in the target intensities is reached divided by the total exercise sessions with valid data excluding the familiarization and the early postoperative phases.

All protocol deviations will be reported and described.

### 3.3. Analysis population

We plan to use two analyses approaches:

- (i) Intention-to-treat: This dataset will be used for the primary analysis of all outcomes and will include all the randomized participants. They will be analyzed based on the group they were originally allocated.
- (ii) Per-protocol analyses: This dataset will be used for secondary analyses and will include participants with >80% of attendance.

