### 1.2. Objective

The overall objective of the ONCOFIT randomized controlled trial is to determine the effects of a multidisciplinary prehabilitation (i.e., 4 weeks before surgery) plus postoperative rehabilitation (i.e., 3 months after surgery) program (PPP) on postoperative complications (as measured by Comprehensive Complication Index (CCI)) in patients undergoing resection of colon cancer.

The secondary aims are to:

- (i) Examine the effects of PPP compared to usual care on clinical prognosis.
- (ii) Examine the effects of PPP compared to usual care on functional capacity.
- (iii) Examine the effects of PPP compared to usual care on body composition.
- (iv) Examine the effects of PPP compared to usual care on fecal microbiota composition.
- (v) Examine the effects of PPP compared to usual care on patient-reported outcomes.
- (vi) Examine the effects of PPP compared to usual care on clinical and tumor parameters.
- (vii) Examine the effects of PPP compared to usual care on lifestyle patterns.
- (viii) Examine the effects of PPP compared to usual care on sleep quality.

[figure not shown]

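### Per-protocol membership depends on attendance during the period when complications accrue, so complications can remove intervention patients and tilt that analysis towards PPP

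*SAP*

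**What the plan says.** Section 3.3 names two analysis populations. Intention-to-treat, with all randomised participants, is primary. Of the per-protocol set it says: "This dataset will be used for secondary analyses and will include participants with >80% of attendance". Section 5.2 repeats the rule in slightly different terms, as a "per-protocol approach, defined as attending >80% of the sessions offered to the intervention group". Neither section exempts any outcome or says how controls enter the set.

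Section 3.2 defines attendance as sessions attended "divided by all the offered sessions (varying on patient preoperative and postoperative periods duration"). The denominator therefore spans both sides of surgery. The same section defines compliance separately, over "total exercise sessions with valid data excluding the familiarization and the early postoperative phases". That exclusion belongs to compliance. It is not applied to attendance, the only measure that decides membership.

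Section 1.2 describes 4 weeks of prehabilitation followed by "postoperative rehabilitation (i.e., 3 months after surgery) program (PPP) on postoperative complications". Section 5.1 takes the primary outcome, CCI, as "obtained by patients at 30 days and 3 months after the surgical procedure", and lists the proportions with any, medical or surgical complications within 30 days, 3 months and 1 year.

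**The concern.** Membership of an analysis set should not depend on the outcome being analysed. Here the attendance window and the complication window overlap for the whole 3 months after surgery. A patient with a serious complication may miss sessions, fall to 80% or below, and leave the intervention arm's set because of the event that the analysis is meant to count. Sessions held after day 30 also help decide who is analysed for 30-day CCI, an outcome already complete by then.

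Controls follow usual care and have no programme sessions described, so nothing comparable removes controls with complications. The loss of high-CCI patients is one-sided. It makes PPP look better in the per-protocol analysis of the trial's central outcome, even with no treatment effect.

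**Working it through.** The SAP gives no figure for this point, so there is none to reproduce. The check has three parts.

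**1. The rule as written.** Attendance covers sessions before and after surgery (3.2). The programme lasts 4 weeks before and 3 months after surgery (1.2). Complications count over the same 3 months (5.1). Attendance above 80% alone decides membership (3.3, 5.2). The SAP sets no cut-off date for attendance, no excused absence for complications and no rule for controls. Membership can therefore depend on the outcome.

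**2. How much absence is enough.** Assume that sessions are evenly spread over 4 + 13 = 17 weeks and stay on offer. A patient who attends a fraction r of sessions when able, and misses m whole weeks, has attendance r(17 − m)/17. This reaches 80%, and so fails the rule, at m = 17 − 0.8 × 17/r:

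- r = 1.0: 17 − 13.6 = 3.4 weeks
- r = 0.9: 17 − 15.1 = 1.9 weeks

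The share of sessions falling after day 30 is (13 − 30/7)/17 = 8.7/17 = 51%.

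**3. Size of the tilt when PPP has no effect.** Only the 45 per arm comes from the SAP (2.3). The assumptions are: 40% complications in both arms; all controls kept; 70% of patients without a complication pass the rule; CCI is 0 without a complication and averages about 20 (minor) or 45 (serious). Let q be the average chance of passing for a patient with a complication.

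- Per-protocol complication rate with PPP = 0.4q / (0.4q + 0.6 × 0.7), against 0.40 in controls
- Spurious odds ratio = q / 0.7

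For example, if half of complications are serious and only those cut passing to 30%, then q = 0.5 × 0.7 + 0.5 × 0.3 = 0.50. The rate is 0.20/0.62 = 0.323 and the odds ratio is 0.50/0.70 = 0.71.

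The last two columns come from simulation (5,000 replicates, two-sided Mann-Whitney test at 0.05).

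| Scenario | q | PPP rate | Odds ratio | CCI difference (points) | False positives |
|---|---|---|---|---|---|
| (a) Attendance unrelated to complications | 0.70 | 0.400 | 1.00 | 0.0 | 5.0% |
| (b) Serious only cut to 30%; serious = 25% of all | 0.60 | 0.364 | 0.86 | 2.2 | 7.3% |
| (b) same, 33% | 0.57 | 0.351 | 0.81 | 2.8 | 7.8% |
| (b) same, 50% | 0.50 | 0.323 | 0.71 | 4.2 | 12.0% |
| (c) Every complication cuts passing to 50% | 0.50 | 0.323 | 0.71 | 2.2 | 9.1% |
| (d) Upper end: every complication cuts it to 30% | 0.30 | 0.222 | 0.43 | 5.0–5.8 | 29.5–30.0% |

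The CCI column agrees with direct arithmetic. In the 50% case the control mean is 0.2 × 20 + 0.2 × 45 = 13.0. The per-protocol mean is (0.14 × 20 + 0.06 × 45)/0.62 = 5.5/0.62 = 8.9. The difference is 4.1, against 4.2 simulated.

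Against the 17.3-point design difference (2.3), cases (b) and (c) run from 2.15/17.3 = 12% to 4.17/17.3 = 24%.

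The result is sensitive to the assumptions. With 80% of uncomplicated patients passing, complication risks of 30–40% and a different CCI distribution, false positives were 22–24% when complications cut passing to 40%, and about 4–5% with no link. Almost all false positives in the linked case favoured PPP.

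**After the change.** Under a rule fixed before surgery and unrelated to the outcome (passing 0.7 for all), the simulated rejection rate was 4.6% and the mean difference 0.0.

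**The case against.** The strongest reply is that little depends on this set. Intention-to-treat is the main analysis for every outcome, and Section 3.1 treats secondary analyses as hypothesis-generating. That limits the consequence, and it stands. It does not remove the bias: the label in Section 3.1 is given as a reason for not adjusting for multiplicity, and a directional error remains in a supportive result.

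Second, the bias needs sessions to count as offered while a patient is recovering. Section 3.2 lets the denominator vary with each patient's preoperative and postoperative periods, so a delayed or shortened programme may shrink it. The session schedule may be in the protocol, which is not at hand. This also stands: the SAP shows that the rule permits the bias, not that the bias will occur. But nothing in the SAP says that sessions missed through a complication are not counted.

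Third, the tilt towards PPP requires that controls are kept. Section 3.3, read literally, gives them no status. However, Section 5.2 ties the threshold to sessions offered to the intervention group, and controls have no programme sessions, so a comparison exists only if they are kept.

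Fourth, the magnitudes rest on assumed rates. The even spread of sessions is doubtful, since Section 3.2 names distinct familiarisation and early postoperative phases. A share of a mean difference also says little about a rank test. All of this is fair, and the figures are illustration only.

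**Conclusion.** The concern holds. As written, the per-protocol rule lets postoperative complications decide which intervention patients are analysed for postoperative complications, and the SAP leaves the status of controls unstated. If complications lower attendance and controls are kept, the per-protocol CCI and complication results favour PPP with no true effect.

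Under the stated assumptions the distortion is modest in cases (b) and (c) and large only in case (d). It is nil if attendance is unrelated to complications or sessions are not offered during recovery, and the SAP does not settle which applies. The primary intention-to-treat analysis is not touched. The point should be fixed before the per-protocol analysis is run, but it does not threaten the trial's main conclusion.

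**What to change.** Add to Sections 3.3 and 5.2:

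> For CCI and the other complication outcomes, the per-protocol set comprises all controls and those intervention patients who attended more than 80% of the sessions offered to them before surgery. The attendance rule applies to the intervention arm only. Postoperative attendance is not an inclusion rule for these outcomes. Results are supportive, because attenders are self-selected.

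This is a wording edit. Trainers already record attendance, and no trial procedure changes. A complication after surgery can then no longer alter membership.

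The price is that, for these outcomes, the set reflects adherence to prehabilitation only and keeps patients who attended little rehabilitation. Self-selection of good attenders also remains, which is why the supportive label is needed.

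A complier-average estimate based on randomisation could be added as a sensitivity analysis, but it is optional. It assumes no effect at or below 80% attendance, which is debatable for a graded exposure, and its interval would be wider.
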